8.2 Responsibility for Analyses/In-House Blinding

The statistical analysis of the data obtained from this study will be the responsibility of the Clinical Biostatistics of the Sponsor. Certain specific analyses such as resistance will be the responsibility of the appropriate department of the Sponsor.

This study will be conducted as a partially randomized and open-label study; therefore, the subjects, the study site personnel, and the Sponsor will be aware of subject treatment assignments after each subject is enrolled.

Throughout the course of this partially randomized and open-label study, efficacy and safety analyses may be performed by the Clinical Biostatistics department of the Sponsor to monitor trends and facilitate programmatic decisions.

8.3 Hypotheses/Estimation

Objectives of the study are stated in Section 3. There will be no efficacy hypothesis testing conducted in this estimation study.

8.4 Analysis Endpoints

Efficacy and safety endpoints that will be evaluated are listed as follows.

8.4.1 Efficacy/Pharmacokinetics Endpoints

8.4.1.1 Efficacy Endpoints

An initial description of efficacy measures is provided in Section 4.2.3.1.

The primary efficacy endpoint is the proportion of subjects achieving SVR₁₂ (sustained virologic response 12 weeks after the end of all study therapy), defined as HCV RNA < LLOQ (either TD[u] or TND).

The secondary efficacy endpoints are:

- The proportion of subjects achieving SVR₁₂, defined as HCV RNA < LLOQ (either TD[u] or TND) in the treatment-naïve F0-F2 subjects.
- The proportion of subjects achieving SVR₂₄ (sustained virologic response 24 weeks after the end of all study therapy), defined as HCV RNA < LLOQ (either TD[u] or TND).
- The viral resistance-associated variants (RAVs) resistant to EBR or GZR, including the association of baseline RAVs with treatment outcomes (SVR₁₂ and SVR₂₄) and the emergence of RAVs in subjects who fail to achieve SVR.

8.4.1.2 Exploratory Endpoints

The exploratory efficacy endpoints are:

- To explore the relationship between *IL28B* genetic variation and:
 - SVR₁₂
 - SVR₂₄
- The relationship between genetic variation and the clinical response to the treatments administered.
- The proportion of anti-HBc positive subjects at screening who develop HBV reactivation (see Section 7.2.3.2).

8.4.2 Safety Endpoints

An initial description of safety measures is provided in Section 4.2.3.2 and events of clinical interest (ECIs) are defined in Section 7.2.3.2. The proportion of subjects who experience AEs of elevated laboratory values that are reported as ECIs described in Section 7.2.3.2 during the study therapy period will be estimated.

The following events will also be investigated: the proportion of subjects with adverse events of the following types at any time during the study therapy period: (1) at least one adverse event; (2) a drug-related adverse event; (3) a serious adverse event; (4) a serious and drug-related adverse event and (5) an adverse event leading to discontinuation.

Other safety parameters include vital signs, physical examinations, and standard laboratory safety tests at time points specified in the Trial Flow Chart (Section 6.0).

Drug related serious adverse events will continue to be collected throughout the study.

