5.2 Trial Treatment(s)

The treatments to be used in this trial are outlined below in [Table 11](#).

Table 11 Trial Treatment

Drug	Weight	Dose/Potency	Dose Frequency	Route of Administration	Regimen/Treatment Period	Use
MK-5172A (fixed dose combination of EBR/GZR)	NA	50 mg/ 100 mg	QD	Oral	Arm 1: 8 weeks Arm 2: 12 weeks	Experimental

The first dose of trial treatment will be administered at the trial site at Visit 2 (Day 1). All other dosing will be performed by the subject (i.e., unsupervised at his/her home) at approximately the same time each day.

The investigator shall take responsibility for and shall take all steps to maintain appropriate records and ensure appropriate supply, storage, handling, distribution and usage of trial treatments in accordance with the protocol and any applicable laws and regulations.

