All adverse events that occur after the consent form is signed but before treatment allocation/randomization must be reported by the investigator if they cause the subject to be excluded from the trial, or are the result of a protocol-specified intervention, including but not limited to washout or discontinuation of usual therapy, diet, placebo treatment or a procedure. From the time of treatment allocation/randomization through 14 days following cessation of treatment, all adverse events must be reported by the investigator. Such events will be recorded at each examination on the Adverse Event case report forms/worksheets. The reporting timeframe for adverse events meeting any serious criteria is described in section 7.2.3.1. The investigator will make every attempt to follow all subjects with non-serious adverse events for outcome.

Electronic reporting procedures can be found in the Electronic Data Capture (EDC) data entry guidelines. Paper reporting procedures can be found in the Investigator Trial File Binder (or equivalent).

7.2.1 Definition of an Overdose for This Protocol and Reporting of Overdose to the Sponsor

In this trial, an overdose is any dose higher than the prescribed dose of EBR/GZR per calendar day.

If an adverse event(s) is associated with (“results from”) the overdose of Sponsor's product or vaccine, the adverse event(s) is reported as a serious adverse event, even if no other seriousness criteria are met.

If a dose of Sponsor's product or vaccine meeting the protocol definition of overdose is taken without any associated clinical symptoms or abnormal laboratory results, the overdose is reported as a non-serious Event of Clinical Interest (ECI), using the terminology “accidental or intentional overdose without adverse effect.”

All reports of overdose with and without an adverse event must be reported by the investigator within 24 hours to the Sponsor either by electronic media or paper. Electronic reporting procedures can be found in the EDC data entry guidelines. Paper reporting procedures can be found in the Investigator Trial File Binder (or equivalent).

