8.5.2 Safety Analysis Population

The All Subjects as Treated (ASaT) population will be used for the analysis of safety data in this study. The ASaT population consists of all subjects who received at least one dose of study treatment. Subjects will be included in the treatment arm corresponding to the study treatment durations they actually received for the analysis of safety data using the ASaT population. The subjects who receive 9 weeks of treatment or less will be summarized in Arm 1 and subjects who receive longer than 9 weeks of treatment will be summarized in Arm 2 for the purposes of safety. Subjects who withdraw study drug early during the treatment period will be included in the treatment arm based on the study treatment duration they actually received.

At least one laboratory or vital sign measurement obtained subsequent to at least one dose of study treatment is required for inclusion in the analysis of each specific parameter. To assess change from baseline, a baseline measurement is also required.

Details on the approach to handling missing data for safety analyses are provided in Section 8.6.2 Statistical Methods for Safety Analyses.

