8.6.2 Statistical Methods for Safety Analyses

Safety and tolerability will be assessed by clinical review of all relevant parameters including adverse experiences and laboratory parameters.

The proportion of subjects with adverse experiences of elevated laboratory values that are reported as ECIs described in Section 7.2.3.2 during the study therapy period are prespecified as events of clinical interest and will be provided.

In addition, the broad clinical and laboratory AE categories consisting of the percentage of subjects with any AE, a drug related AE, a serious AE, an AE which is both drug-related and serious, and who discontinued due to an AE will be summarized in the same manner (Table 16). Laboratory parameters will be summarized by pre-defined limits of change, laboratory grade shift summaries, and for selected laboratory parameters, change from baseline summaries.

In this estimation study, rates of events of clinical interest (as defined in Section 7.2.3.2) as well as broad categories of adverse events will be reported along with 95% confidence intervals for safety monitoring. Rates will also be shown for all specific AEs reported and pre-determined limits of change in laboratory results.

Missing safety parameter values will be handled using the Data-As-Observed (DAO) approach, that is, any missing value will be excluded from the analysis. For lab shift summaries, change from baseline summaries and certain pre-defined limits of change summaries require a baseline value. If a baseline value is missing, the latest pre-treatment value will be used instead. If no pre-treatment result is available, that subject will not be included in the summary. The safety summarization of results will be presented by treatment arm (Arm 1 and Arm 2) unless otherwise specified.

Table 16 Analysis Strategy for Safety Parameters

Safety Endpoint [†]	95% CI [‡]	Descriptive Statistics
AEs of elevated laboratory values that are reported as ECIs	X	X
Any AE	X	X
Any SAE	X	X
Any drug-related AE	X	X
Any serious and drug-related AE	X	X
Discontinuation due to AE	X	X
Specific AEs, SOCs, or PDLCs Change from baseline results (laboratory results, vital signs)		X X

AE = adverse event; CI = confidence interval; ECI = clinical event of interest; PDLC = pre-defined limit of change; SOC = system organ class; X = results will be provided.
† Adverse experience references refer to both clinical and laboratory AEs.

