8.12 Extent of Exposure

The Extent of Exposure to study treatment will be evaluated by summary statistics (N, mean and range) for the “Number of Days on Therapy” by treatment group.

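### AE and laboratory-ECI results are planned only as crude per-arm proportions over 8 v 12 weeks, so most categories would tend to look lower in the 8-week arm at equal weekly risk

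*Combined protocol and SAP*

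**What the plan says.** Table 11 (Section 5.2) gives one daily fixed-dose tablet in both arms, with durations "Arm 1: 8 weeks Arm 2: 12 weeks".

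Section 8.4.2 defines five broad AE categories (any, drug-related, serious, serious and drug-related, leading to discontinuation) as "the proportion of subjects with adverse events of the following types at any time during the study therapy period". For laboratory events, the proportion with "AEs of elevated laboratory values that are reported as ECIs described in Section 7.2.3.2 during the study therapy period will be estimated".

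Section 8.6.2 sets the layout: "The safety summarization of results will be presented by treatment arm (Arm 1 and Arm 2) unless otherwise specified". It adds that "broad categories of adverse events will be reported along with 95% confidence intervals for safety monitoring", and Table 16 lists the same endpoints. Section 8.12 summarizes days on therapy by treatment group but does not connect them to adverse events.

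Two other passages decide what the proportions mean. Section 7.2 runs collection beyond the last dose: "From the time of treatment allocation/randomization through 14 days following cessation of treatment, all adverse events must be reported by the investigator". The term study therapy period is not defined, so it is unclear whether those 14 days count. Section 8.5.2 assigns safety arms by duration received: "The subjects who receive 9 weeks of treatment or less will be summarized in Arm 1". That includes Arm 2 subjects who stop early.

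**The concern.** Safety and tolerability is the second primary objective (Section 3.1), and Section 4.2.1.2 presents the trial partly as a test of whether a shorter 8-week regimen is viable. A proportion with at least one event cannot fall as observation lengthens. The planned tables therefore cannot tell fewer events because observation was shorter from fewer events because the drug was better tolerated.

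Detection of laboratory events is also uneven. The flow chart (Section 6.0) has on-treatment laboratory visits at Weeks 4 and 8 in Arm 1 and at Weeks 4, 8 and 12 in Arm 2. The next scheduled visit, FU4, opens no earlier than 3 weeks after treatment, beyond the 14-day reporting window. That leaves two scheduled post-baseline chances against three to find a transaminase ECI.

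**Working it through.** **The plan's own figures.** Table 18 is the upper limit of the two-sided 95% Clopper-Pearson interval. For zero events it is 1 − 0.025^(1/n): 7.1% at n = 50 and 5.1% at n = 70, as printed. All 15 bounds reproduce. They describe precision within an arm and say nothing about unequal windows.

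**Inputs.** Durations of 8 and 12 weeks (Table 11); about 10 and 14 weeks with the tail (Section 7.2); targets of 50 and 70 (Section 8.9.1). AE incidence and hazard shape are not in the documents, so the values below are assumptions.

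**Equal constant weekly hazard.** If P is the proportion affected in Arm 2, Arm 1 shows 1 − (1 − P)^(8/12). With the tail, the exponent is 10/14 and P refers to 14 weeks.

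| Arm 2 | Arm 1, 8 v 12 weeks | Gap (points) | Arm 1, 10 v 14 weeks | Gap (points) |
|---|---|---|---|---|
| 5% | 3.4% | 1.6 | 3.6% | 1.4 |
| 40% | 28.9% | 11.1 | 30.6% | 9.4 |
| 60% | 45.7% | 14.3 | 48.0% | 12.0 |
| 70% | 55.2% | 14.8 | 57.7% | 12.3 |
| 80% | 65.8% | 14.2 | 68.3% | 11.7 |

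A person-time rate would be equal in the two arms by construction. At P = 50% it is −ln(0.5)/12 = 0.058 per week, or 5.8 first events per 100 person-weeks at risk.

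**Front-loaded hazard.** If 90% of the 12-week cumulative hazard falls in the first 8 weeks, the exponent is 0.9. At P = 70%, Arm 1 shows 1 − 0.3^0.9 = 66.2%, a gap of 3.8 points. If every first event falls by Week 8, there is no gap.

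**Effect of the 9-week rule on discontinuation due to AE.** Assume a 12-week probability of 3% and a constant hazard: h = −ln(0.97)/12 = 0.00254 per week.

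- Arm 1 stoppers: 50 × (1 − e^(−8h)) = 1.01.
- Arm 2 stoppers by Week 9, moved to Arm 1: 70 × (1 − e^(−9h)) = 1.58.
- Arm 2 stoppers after Week 9: 70 × (e^(−9h) − e^(−12h)) = 0.52.
- Safety Arm 1: (1.01 + 1.58)/51.58 = 5.0%.
- Safety Arm 2: 0.52/68.42 = 0.8%.

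By assigned arm the figures would be 2.0% and 3.0%. The rule reverses the order.

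**SAEs.** With a 12-week SAE probability of 3% and a share of SAEs stopping treatment at once, the as-treated figures for Arm 1 and Arm 2 are 2.0% v 3.0% at a share of 0, 2.6% v 2.6% at 20%, and 3.5% v 1.9% at 50%. Either order is possible.

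**Any AE under the rule.** At 70% affected and 3% stopping for an AE, the as-treated figures are 56.6% v 69.3%. The gap narrows from 14.8 to 12.7 points but keeps its direction.

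**The case against.** Duration is the intervention, so risk per course is a proper quantity to report. The study is for estimation, and no between-arm safety test or difference is planned. The arms are openly labelled 8 and 12 weeks. By target, 45 of the 70 Arm 2 subjects are non-randomized TN F3-F4 or TE, so whole arms are not comparable even after exposure adjustment. The size rests on assumed incidence, and even in the 60% scenario the exact intervals overlap: 23/50 gives 31.8% to 60.7%, and 42/70 gives 47.6% to 71.5%.

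Most of this stands, and it shapes the remedy. The per-course proportions should stay. The harm is to side-by-side reading, not to a planned test. Adding exposure-adjusted columns to the existing safety arms would not be enough: after the 9-week rule, safety Arm 2 holds only subjects who passed 9 weeks on drug, and case mix differs. What the objection does not answer is that nothing planned lets a reader separate duration from tolerability, although the 2:1 randomized TN F0-F2 subjects would allow it.

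A reader might infer that every AE endpoint favours the 8-week arm, or that 11 to 14 points is the bias to expect. The documents support neither. Section 8.5.2 reverses the order for discontinuation due to AE and can reverse it for SAEs, and the documents give neither an incidence nor a hazard shape.

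**Conclusion.** The concern holds in a limited form. Every AE and laboratory-ECI endpoint is a crude per-arm proportion over periods that differ by design, with no common window or person-time summary. For any AE, drug-related AE, specific AEs and, subject to timing, laboratory ECIs, the 8-week arm would tend to look lower at equal weekly risk.

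The size is conditional: 11 to 14 points under constant hazard with 40% to 80% of Arm 2 affected, 9 to 12 points with the tail, about 4 points in the front-loaded case at 70%, and under 2 points for an event at 5%. It requires first events to keep arising after Week 8. No uniform direction can be claimed for discontinuation due to AE or for SAEs. This is an inexpensive improvement to how a primary objective is reported; it does not invalidate the per-course figures.

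**What to change.** 1. In Section 8.4.2, state whether the study therapy period includes the 14 days after the last dose.
2. In Section 8.6.2 and Table 16, keep the per-course proportions. For each broad AE category and the laboratory ECIs, add the proportion with onset from Day 1 through Day 56, with 95% CI, by assigned arm and not by duration received. The flow chart lets the Week 8 visit fall up to 14 days late, so state whether a laboratory ECI found at such a visit counts.
3. As a supplement, give the exposure-adjusted incidence to first event (subjects with an event per 100 person-weeks at risk) with 95% CI, also by assigned arm.
4. Show these summaries separately for the randomized TN F0-F2 subjects (about 50 v 25), because whole-arm figures remain confounded by the non-randomized F3-F4 and TE subjects.

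**Cost.** SAP wording and a few table columns. AE start dates (Table 13), last-dose dates for subjects who stop early (Section 7.1.5.4) and days on therapy (Section 8.12) are already collected, and Section 8.0 allows a supplemental SAP before database lock. Conduct and sample size do not change. The price is imprecision: 15/25 affected (60%) has an exact 95% CI of 38.7% to 78.9%, so the randomized subset will describe the pattern without settling it.

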8.5 Analysis Populations

8.5.1 Efficacy Analysis Population

The Full Analysis Set (FAS) population will serve as the primary population for the analysis of efficacy data in this study. The FAS population consists of all subjects who were assigned to a treatment arm and received at least one dose of study treatment.

A supportive analysis using the modified Full Analysis Set (mFAS) population will be performed for the primary (SVR_{12}) and key secondary efficacy endpoint (SVR_{24}). The mFAS population is a subset of the FAS, with subjects excluded for study discontinuation (lost to follow-up) with reasons unrelated to the treatment regimen. Examples of reasons for the exclusion of a subject include: failure to receive at least one dose of study treatment; loss to follow-up; missing data due to death with reasons unrelated to the study drug; discontinuation due to non-drug related AEs; informed consent and withdrawal.

Resistance Analysis (RA) Population will be used for resistance-associated variants (RAVs) analysis. The RA population is a subset of FAS, who either achieved SVR_{12} or met criteria for virologic failure (see Section 4). The RA does not include any subject who discontinued the study for reasons other than virologic failure. Baseline RAV analyses will be conducted in subjects for whom baseline sequencing data was available. Post-baseline RAV analyses will be limited to subjects who had both baseline and post-failure sequence data.

Details on the approach to handling missing data are provided in Section 8.6.1.

8.5.2 Safety Analysis Population

The All Subjects as Treated (ASaT) population will be used for the analysis of safety data in this study. The ASaT population consists of all subjects who received at least one dose of study treatment. Subjects will be included in the treatment arm corresponding to the study treatment durations they actually received for the analysis of safety data using the ASaT population. The subjects who receive 9 weeks of treatment or less will be summarized in Arm 1 and subjects who receive longer than 9 weeks of treatment will be summarized in Arm 2 for the purposes of safety. Subjects who withdraw study drug early during the treatment period will be included in the treatment arm based on the study treatment duration they actually received.

At least one laboratory or vital sign measurement obtained subsequent to at least one dose of study treatment is required for inclusion in the analysis of each specific parameter. To assess change from baseline, a baseline measurement is also required.

Details on the approach to handling missing data for safety analyses are provided in Section 8.6.2 Statistical Methods for Safety Analyses.

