3.1 Primary Objective(s) & Hypothesis(es)

- (1) To evaluate the efficacy of each treatment arm of EBR/GZR as assessed by the proportion of subjects achieving SVR₁₂ [sustained virologic response defined as HCV RNA < Lower Limit of Quantitation (LLOQ) 12 weeks after the end of all study therapy].
- (2) To evaluate the safety and tolerability of EBR/GZR.

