8.1 Statistical Analysis Plan Summary

This section contains a brief summary of the statistical analyses for this trial. Full detail is provided in 8.2-8.12.

Study Design Overview	A Multi-Site, Open-Label, Partially-Randomized Trial of the Efficacy and Safety of Fixed Dose Elbasvir/Grazoprevir (EBR/GZR) Based Regimens in French Subjects with Chronic Hepatitis C Virus (HCV) Genotype 4 Infection
Treatment Assignment	This study will enroll approximately 120 genotype 4 (GT4) HCV subjects with or without advanced fibrosis. There are 2 treatment arms in this study. Approximately 75 (minimum of 60) TN subjects with stage 0-2 fibrosis will be randomized using a 2:1 ratio to receive either 8 weeks of EBR/GZR (Arm 1) or 12 weeks of EBR/GZR (Arm 2). TN subjects with stage 3-4 fibrosis and TE subjects with stage 0-4 fibrosis will be assigned to Arm 2 to receive 12 weeks of EBR/GZR. The target enrollment in each group is: Study Arm 1: 8-week regimen of EBR/GZR TN subjects with fibrosis stage F0-F2 n=50 (min 40) Study Arm 2: 12-week regimen of EBR/GZR TN subjects with fibrosis stage F0-F2 n=25 (min 20) TN subjects with fibrosis stage F3-F4 n=25 (min 15) TE subjects with fibrosis stage F0-F4 n=20 (min 15)
Analysis Populations	Efficacy: The Full Analysis Set (FAS) population will serve as the primary population for the analysis of efficacy data in this study. The FAS population consists of all subjects who were assigned to a treatment arm and received at least one dose of study treatment. A supportive analysis using the modified Full Analysis Set (mFAS) population will be performed for the primary efficacy and secondary endpoints. The mFAS population is a subset of the FAS, with subjects excluded for study discontinuation (lost to follow-up) with reasons unrelated to the treatment regimen. Safety: The All Subjects as Treated (ASaT) population will be used for the analysis of safety data in this study. The ASaT population consists of all subjects who received at least one dose of study treatment, classified according to the study treatment duration they actually received.

Primary Endpoint(s)	Proportion of subjects achieving SVR ₁₂ (Sustained Virologic Response 12 weeks after the end of all study therapy).
Key Secondary Endpoints	Proportion of subjects achieving SVR ₂₄ (Sustained Virologic Response 24 weeks after the end of all study therapy).

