8.6.3 Summaries of Baseline Characteristics, Demographics, and Other Analyses

Demographic and Baseline Characteristics

No statistical hypothesis tests will be performed on these characteristics. The number and percentage of subjects screened, enrolled, the primary reasons for screen failure, and the primary reason for discontinuation will be displayed. Demographic variables (e.g., age, gender, and genotype subtype), primary and secondary diagnoses, and prior and concomitant therapies will be summarized using descriptive statistics for continuous or categorical variables, as appropriate. Summary statistics for the baseline efficacy measure (HCV RNA) will also be provided.

Viral Resistance Measurements

Viral resistance testing will focus on the entire NS3/4A and NS5A regions for all subjects and for those who meet the subject virologic failure criteria (see Section 4.2.3.1.1.2).

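### Safety arm is set by weeks of drug taken, so Arm 2 subjects who stop for an adverse event by week 9 are counted in Arm 1, which distorts the by-arm rate of discontinuation due to AE

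*Combined protocol and SAP*

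**What the plan says.** Section 8.5.2 defines the All Subjects as Treated population as everyone who took at least one dose, and then sets the arm by time on drug: "The subjects who receive 9 weeks of treatment or less will be summarized in Arm 1", while "subjects who receive longer than 9 weeks of treatment will be summarized in Arm 2". It makes no exception for people who stop early, who are placed by their realised time on drug: "Subjects who withdraw study drug early during the treatment period will be included in the treatment arm based on the study treatment duration". The summary in Section 8.1 repeats the rule, with subjects "classified according to the study treatment duration they actually received".

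Section 8.4.2 lists "an adverse event leading to discontinuation" among the safety endpoints, and Table 16 gives it a 95% confidence interval. Section 8.6.2 states: "The safety summarization of results will be presented by treatment arm (Arm 1 and Arm 2) unless otherwise specified". Section 8.6.3 adds that "the primary reason for discontinuation will be displayed", without saying how arms are formed for that display. No safety table by assigned arm is specified.

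**The concern.** Table 11 shows one tablet, one dose and one frequency for both arms; only the planned duration differs. A subject assigned 12 weeks who stops in week 3 was given nothing belonging to the other arm. The usual reason for an as-treated move, that the subject received the other treatment, does not apply.

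For discontinuation due to AE, the grouping depends on the outcome being counted. Remaining on drug for more than 9 weeks is a condition of entry to safety Arm 2, so an Arm 2 stop can appear there only if it falls in the last 3 of 12 weeks. Arm 1 collects its own AE stops plus the early ones from Arm 2. The Arm 1 rate rises and the Arm 2 rate falls, provided AE stops are a larger share of the moved subjects than of the arm they join or leave. No direction is claimed for the rates of any AE, serious AEs or events of clinical interest.

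Primary objective 2 in Section 3.1 reads "To evaluate the safety and tolerability of EBR/GZR", and Section 4.2.1.2 asks whether an 8-week regimen is viable in F0-F2 subjects. Readers will look at tolerability by regimen. Arm 1, which by design enrols only treatment-naïve F0-F2 subjects, could also come to contain treatment-experienced or F3-F4 subjects in its safety tables.

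**Working it through.** **The plan's own figures.** The Table 18 bounds are upper limits of two-sided 95% Clopper-Pearson intervals. For 0/50 the bound is 1 − 0.025^(1/50) = 7.1%, as printed. All 15 entries reproduce to 0.1 point. The same method is used below.

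**Inputs from the documents.** Expected arm sizes are 50 and 70 (Section 8.9), planned durations are 56 and 84 days (Table 11), and the cut is 63 days (Section 8.5.2).

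**Assumed inputs.** The documents give neither a rate nor a timing of AE stops for this trial. I take a 12-week AE-stop risk p of 1%, 2% or 4%. The timing curve F(t), the share of 12-week AE stops that have occurred by day t, is the same in both arms.

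**Formulae.**
- True Arm 1 risk: p1 = p × F(56). Under constant hazard F(56) = 56/84 = 0.667.
- Share of Arm 2 AE stops that move: q = F(63) = 63/84 = 0.75.
- Number moved: m ~ Binomial(70, pq), with mean 70pq and P(m = 0) = (1 − pq)^70.
- Reported Arm 1 rate, on average: E[(50·p1 + m)/(50 + m)].
- Reported Arm 2 rate: p(1 − q)/(1 − pq).

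For p = 2%, pq = 0.015. The mean moved is 70 × 0.015 = 1.05, P(m = 0) = 0.985^70 = 0.35, and the reported Arm 2 rate is 0.02 × 0.25/0.985 = 0.51%. Exact enumeration gives 3.33% for Arm 1.

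**Results, constant hazard (Arm 1 vs Arm 2).**

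| p over 12 weeks | By assigned arm | As the plan reports | Mean moved | P(nobody moves) | P(Arm 1 lower as assigned, higher as reported) |
|---|---|---|---|---|---|
| 1% | 0.67% vs 1% | 1.7% vs 0.3% | 0.5 | 59% | 33% |
| 2% | 1.3% vs 2% | 3.3% vs 0.5% | 1.05 | 35% | 48% |
| 4% | 2.7% vs 4% | 6.5% vs 1.0% | 2.1 | 12% | 62% |

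**Other timing (reported rates for p = 1%, 2%, 4%).**
- Half the stops in the first 4 weeks, the rest spread evenly (F(56) = 0.75, F(63) = 0.8125): 1.8 vs 0.2, 3.7 vs 0.4, 7.1 vs 0.8.
- Hazard rising in proportion to time, F = (t/84)² (0.444 and 0.5625): 1.2 vs 0.4, 2.4 vs 0.9, 4.7 vs 1.8.

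**Other checks.**
- If the 8-week regimen carried no AE-stop risk at all, Arm 1 would still show 1.0%, 2.0% or 4.0% under constant hazard.
- Adding non-AE stops at 10% over 12 weeks, which move too and dilute the effect, gives 1.5 vs 0.3, 3.0 vs 0.55 and 5.9 vs 1.1.

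**Worked counts.**
- One AE stop, in Arm 2 before week 9. By assignment: 0/50 (95% CI 0 to 7.1%) vs 1/70 = 1.4% (0.04 to 7.7%). Under the plan: 1/51 = 2.0% (0.05 to 10.4%) vs 0/69 (0 to 5.2%).
- One AE stop in Arm 1 and three in Arm 2, two of them by week 9. By assignment: 1/50 = 2.0% (0.1 to 10.6%) vs 3/70 = 4.3% (0.9 to 12.0%). Under the plan: 3/52 = 5.8% (1.2 to 15.9%) vs 1/68 = 1.5% (0.04 to 7.9%).

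Table 3 shows that such stops occur: with 12 weeks and no ribavirin, one AE stop among 9 treatment-experienced subjects and none listed among 56 treatment-naïve. Section 4.2.2.3 says the event was not drug related and does not give its timing, so it is not used as a rate.

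**The case against.** The strongest reply is that this is a declared choice of target. The population is named as-treated, the rule is stated twice and consistently, and safety by realised exposure is something one may want to know. That does not rescue this endpoint. A rate of stopping among people grouped by when they stopped is not a discontinuation rate for either regimen.

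A second reply is that little rests on the contrast between arms. Objective 2 does not say it is by arm, no hypothesis is tested, and about 45 of the 70 Arm 2 subjects are assigned rather than randomised (Section 5.3), so the arms are not fully comparable even by assignment. All of that stands and limits the severity. It is not a reason to add avoidable misclassification to rates that the plan intends to publish with intervals.

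Third, the size is assumed. At a 12-week risk of 0.5%, nobody would move with probability 77%, and one or two events decide the order of the arms, with wide and overlapping intervals. This also stands: the direction is secure, the size is not.

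Fourth, the cut might serve Arm 1 subjects who over-run. They receive five 14-day cards (70 days of drug for a 56-day regimen; Sections 6.0 and 9.2), and the Week 8 window extends to +14 days. The documents do not give this as the reason for 9 weeks, and a subject assigned 8 weeks who takes surplus tablets still belongs in Arm 1.

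Finally, the disposition display and the exposure summary in Section 8.12 mean AE stops are not hidden. Neither states its arm rule, so neither corrects the by-arm rate.

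**Conclusion.** The concern holds and should be fixed. As written, the by-arm rate of discontinuation due to AE and its interval do not describe either regimen. Arm 1 is biased upward and Arm 2 downward, and under constant hazard the regimen with the higher true rate is reported on average as having the lower one. For assumed 12-week risks of 1% to 4%, the reported Arm 1 rate is about 2.4 to 2.5 times its assigned-arm value (1.68/0.67 = 2.5; 6.52/2.67 = 2.4), and the Arm 2 rate is about a quarter of its own (0.25/1; 1.03/4). Both alternative timings shift the two arms in the same directions. In counts the effect is about 0.5 to 2 subjects on average, and it is zero if no Arm 2 subject stops by week 9. Pooled safety and all efficacy results are untouched.

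**What to change.** In Section 8.5.2, remove the 9-week cut and the sentence on early withdrawal, and replace the duration-based assignment with: *ASaT safety data will be summarised by assigned regimen. A subject is moved to the other arm only if IVRS/IWRS and dispensing records show that the other arm's regimen was given in error; stopping early is never a reason to move a subject.* In Section 8.1, replace the clause on duration received with: *classified by assigned regimen (see Section 8.5.2)*. A table by realised duration may stay as a supplement beside the exposure summary in Section 8.12.

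The cost is three sentences in 8.5.2 and one clause in 8.1. No new data are needed, because assignment is already held in the IVRS/IWRS, and Section 8.0 allows the change through a supplemental SAP before database lock. The one consequence for the sponsor is that Arm 2's discontinuation rate may look slightly less favourable.
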